#### **8.5.4.9 Unscheduled Study Visit for Study Period 1 or Study Period 2**

The following procedures may be conducted at any Unscheduled Study Visit that occurs during Study Period 1 or Study Period 2:

- Body weight
- IMP assignment, if weight change ( $> 2$  kg) requires dose volume adjustment
- Vital signs
- Safety assessments
- Collection of urine sample for hCG pregnancy test, if applicable
- Collection of blood samples for exploratory biomarkers (serum analysis)
- Collection of blood samples to assess the following:
  - Hematology
  - Muscle enzymes
  - Other biochemistry
  - Coagulation
  - Serum IgG
- Subject SC Infusion Diary review
- Document AEs

- Document concomitant therapies
- Document any change to physiotherapy since the previous study visit
- DOW assessment if before Week 25 (Note: 2 consecutive assessments must be at least 2 weeks apart to meet the criteria for DOW.)
- Assess if subject has clinically relevant improvement, and if so, initiate oral corticosteroid taper
- Individual CSMs
- CDASI
- SC infusion, if applicable, at Week 3 or Week 4 only

## 8.5.5 Study Period 3

During Study Period 3, subjects will be treated with open-label IgPro20 at 0.5 g/kg SC on a weekly basis and subjects will be asked to return to the study site to complete safety assessments and measurement of body weight on a monthly basis as specified in the Schedule of Assessments for Study Period 3 ([Table 3](#)). Additionally, efficacy assessments will be performed at 6-month and 12-month intervals during the subject's continued participation in Study Period 3. Adverse events and concomitant medications will be assessed throughout the subject's participation in the study.

If a subject is withdrawn from the study before completing the EOP3 Visit, all EOP3 Visit assessments should be performed at the last study visit.

### 8.5.5.1 Monthly (every 4 weeks) Study Visits

The following procedures will be conducted at each monthly study visit ( $\pm$  7 days) during Study Period 3:

- Body weight
- IMP assignment (weight change of  $>2\text{kg}$  requires dose volume adjustment)
- Subject SC Infusion Diary review
- Document AEs
- Document concomitant therapies

### 8.5.5.2 Study Visits Every 6 Months (24 weeks)

In addition to assessments collected at monthly visits, the following will be conducted every 6 months (24 weeks):

- Collection of urine sample for hCG pregnancy test, if applicable
- Vital signs
- Body weight
- Efficacy Assessment (4 Individual CSMs):
  - Physician Global VAS
  - Patient Global VAS
  - MMT-8
  - HAQ
- CDASI
- EQ-5D-5L
- IMP assignment
- IMP SC weekly infusions
- Subject SC infusion diary review

### 8.5.5.3 End of Year Visit

During participation in Study Period 3, subjects may continue treatment with open-label IgPro20 0.5 g/kg SC weekly until the end of the study (see [Section 3.7](#)). At scheduled study visits at the end of each year ( $\pm$  7 days) during the subject's participation in Study Period 3, the following assessments will be performed in addition to the assessments specified for the study visits every month (see [Section 8.5.5.2](#)):

- Collection of urine sample for hCG pregnancy test, if applicable
- General physical examination
- Vital signs
- Collection of blood samples to assess the following:
  - Hematology
  - Biochemistry
- Efficacy Assessment (4 Individual CSMs):
  - Physician Global VAS
  - Patient Global VAS
  - MMT-8
  - HAQ
- CDASI
- EQ-5D-5L
- IMP Assignment for subjects continuing in Study Period 3
- IMP SC weekly infusions for subjects continuing in Study Period 3
- Document reason for withdrawal, if applicable

#### 8.5.5.4 End of Period 3 Visit

If a subject is withdrawn from the study at any time during Study Period 3, the investigator should make every effort to perform the assessments scheduled for the EOP3 Visit:

- Collection of urine sample for hCG pregnancy test, if applicable
- General physical examination
- Vital signs
- Body weight
- Collection of blood samples for virology retention
- Collection of blood samples to assess the following:
  - Hematology
  - Biochemistry
- Subject SC Infusion Diary review
- Document AEs
- Document concomitant therapies
- Efficacy Assessment (4 Individual CSMs):
  - Physician Global VAS
  - Patient Global VAS
  - MMT-8
  - HAQ
- CDASI
- EQ-5D-5L
- Document reason for withdrawal, if applicable

### 8.5.5.5 Unscheduled Study Visit for Study Period 3

The following procedures may be performed at any Unscheduled Study Visit that occurs during Study Period 3:

- Collection of urine sample for hCG pregnancy test, if applicable
- Vital signs
- Body weight
- IMP assignment, if weight change (> 2 kg) requires dose volume adjustment
- Safety assessments
- Collection of blood samples to assess the following:
  - Hematology
  - Biochemistry
- Subject SC Infusion Diary review
- Document AEs
- Document concomitant therapies
- Efficacy Assessments (4 Individual CSMs):
  - Physician Global VAS
  - Patient Global VAS
  - MMT-8
  - HAQ
- CDASI
- EQ-5D-5L
- Document reason for withdrawal, if applicable

## 8.5.6 Discontinuation of IMP

Subjects may discontinue IMP at any time at their own request or at the discretion of the investigator. The investigator should record in the eCRF and in the subject's medical records the reason and date of IMP discontinuation.

Subjects who discontinue IMP will be encouraged to remain in the study until Week 25 if discontinuation occurs before Week 25, or until Week 53, if discontinuation occurs after Week 25, in order to collect study assessments.

If the subject discontinues IMP during Study Period 1 or Study Period 2, all Week 53 assessments (see [Section 8.5.4.7](#)) will be performed at the study visit where IMP treatment is discontinued, instead of the assessments scheduled for that particular study visit. If subjects discontinue IMP during Study Period 3, subjects will be withdrawn from the study after they have completed the EOP3 Visit assessments.

See the [Schedule of Assessments](#) for details on assessments no longer collected after IMP discontinuation if the subject remains in the study.

## 9 Adverse Events

### 9.1 Definitions

#### 9.1.1 Adverse Event

As per the ICH Topic E2A (Clinical Safety Data Management: Definitions and Standards for Expedited Reporting), an AE is any untoward medical occurrence in a patient or clinical investigation subject administered a pharmaceutical product and which does not necessarily have a causal relationship with this treatment. An AE can, therefore, be any unfavorable and unintended sign (including an abnormal, clinically significant laboratory finding), symptom, or disease temporally associated with the use of a medicinal (investigational) product, whether or not considered related to the medicinal (investigational) product.

The period of observation for AEs extends from the time the subject gives informed consent until the end of study participation (see [Section 9.4](#) for further details).

---

Adverse events may include:

Exacerbation (ie, an increase in the frequency or severity) of a pre-existing condition, with the exception of DM

- Illness present before study entry should be recorded in the medical history section of the eCRF and only be reported as an AE if there is an increase in the frequency or severity of the condition during the study

A clinical event occurring after consent but before IMP administration

Intercurrent illnesses with an onset after administration of IMP

Adverse events do not include:

Any worsening of DM including worsening of DM that meets serious criteria (eg, hospitalization)

Events identified at Screening that meet exclusion criteria

Medical or surgical procedures (the condition that leads to the procedure is the AE)

Situations where an untoward medical occurrence has not taken place, eg:

- Planned hospitalizations due to pre-existing conditions, which have not worsened
- Hospitalizations that occur for procedures not due to an AE (eg, cosmetic surgery)
- Hospitalizations for a diagnostic procedure where the hospital stay is less than 24 hours in duration or for normal management procedures (eg, chemotherapy)
- Overdose of IMP or any concomitant therapy that does not result in any adverse signs or symptoms

For laboratory safety parameters, any instances of absolute values being outside the reference range or changes at any study visit after the start of the study that are considered by the investigator as clinically significant must be recorded in the eCRF as AEs. In addition, at the investigator's discretion, any changes or trends over time in laboratory parameters can be recorded in the eCRF as AEs if such changes or trends are considered to be clinically relevant, even if the absolute values are within the reference range.

Laboratory findings do not need to be reported as AEs in the following cases:

Laboratory parameters already beyond the reference range at Screening, unless a further increase/decrease can be considered an exacerbation of a pre-existing condition

Abnormal laboratory parameters caused by mechanical or physical influences on the blood sample (eg, in vitro hemolysis) and flagged as such by the laboratory in the laboratory report

Abnormal parameters that are obviously biologically implausible (eg, values that are incompatible with life or outside the measuring range)

An abnormal laboratory value that cannot be confirmed after repeat analysis, preferably in the same laboratory (ie, the previous result could be marked as not valid and should not necessarily be reported as an AE)

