### 3.8.2 Independent Data Monitoring Committee

The independent data monitoring committee (IDMC) will monitor the efficacy and safety data generated during Study Period 1 and Study Period 2 (through Week 53 / Week 56) in order to conduct assessments of the benefit-risk profile. The IDMC will consist of external experts in the fields of dermatology, rheumatology, neurology, hematology/coagulation, and statistics who have experience treating patients with DM and/or experience in clinical studies. The IDMC will receive notification of all serious adverse events (SAEs), AESIs, and deaths reported throughout the study. In addition, the IDMC will meet at regularly scheduled intervals to evaluate compiled efficacy and safety data to assess overall benefit-risk. After each meeting, recommendations will be issued to CSLB regarding the continuation of the study, potential need for protocol modifications, or study termination. No success or futility thresholds will be set for the IDMC reviews; CSLB will not stop the study based on these data unless a major safety issue has been identified (see Section 3.9). The composition, activities, and responsibilities of the IDMC will be described in the IDMC Charter.

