### 9.1.2 Serious Adverse Event

An SAE is defined as any untoward medical occurrence that at any dose:

**Results in death** – The event must be the cause of death for the SAE to meet this serious criterion

**Is life-threatening** – The term “life-threatening” refers to an event in which the subject was at risk of death at the time of the event; it does not refer to an event that hypothetically might have caused death if it had been more severe

**Requires in-patient hospitalization or prolongation of existing hospitalization** – CSLB considers “hospitalization or prolongation of existing hospitalization” for at least 24 hours as the defining criterion for an SAE. Hospital admissions for planned surgery or for normal disease management procedures (eg, chemotherapy) are not considered as defining criteria for SAEs

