#### Subject Disposition: Study Treatment Discontinuation or Study Discontinuation

Subjects who experience either study treatment discontinuation or study discontinuation due to COVID-19 will have the reason captured in the eCRF. On the appropriate eCRF form to record either study medication discontinuation (“End of Treatment” and / or “End of Treatment Period 3” form) or study discontinuation (“Conclusion of Subject Participation” form), a reason will be selected which includes a field for descriptive text. The reason can be either “Withdrawal by Subject,” “Physician Decision,” or “Other”. The associated free text field entry will include “COVID-19”. When either treatment or the study is discontinued due to an AE or death, the

specific corresponding AE is collected. Discontinuations due to COVID-19 adverse events will then be identified based on whether the MedDRA code for the AE is included in the broad COVID-19 standard MedDRA query (SMQ).

Cases of study treatment discontinuation or study discontinuation due to COVID-19 will be included in the summary of subject disposition.

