### 8.2.17 DOW

A subject who meets at least 1 of the following 3 criteria on 2 consecutive study visits at least 2 weeks apart, as compared to reference visit will be considered to have met the DOW.

- Physician Global Disease Activity Assessment VAS (CSM 1) worsening  $\geq 2$  cm\* and MMT-8 worsening (CSM 3)  $\geq$  absolute 10%, or
- Extramuscular Global Assessment VAS worsening (CSM 6)  $\geq 2$  cm, or
- Any 3 of 6 CSM worsening by  $\geq$  absolute 20%.

\* If baseline Physician Global VAS is 8-10, then any worsening on Physician Global VAS is acceptable as long as MMT-8 criterion is met.

The reference visit for DOW is the baseline visit.

Clinical worsening according to DOW is finished at the first subsequent study visit where none of the criteria are met. A potential next DOW and possible rescue oral corticosteroid treatment can start only after the end of the preceding DOW.

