## 11.2 Adverse Events

Adverse events will be coded using the Medical Dictionary for Regulatory Activities (MedDRA) version 21.0 or higher. TEAEs are defined as AEs started after the start of the first infusion of IMP. All AEs regardless of when they were reported will be listed.

In addition to an overall TEAE analysis, the analysis will be repeated for each period. An AE will be counted in the respective analysis, if the onset of the event falls within the period. For the definition of start and end of the periods see [Table 8](#) and [Table 9](#).

- An overview summary of TEAEs, including number of subjects, percentages of subjects, the number of events, and TEAE rate per time at risk, including the following. This summary will also be provided for the subgroup of Japanese subjects and by age group (<65 year, ≥65 years):
  - Any TEAE
  - TEAEs related to IMP
  - TEAEs related to corticosteroid treatment

- Temporally associated TEAEs (defined as an AE with an onset between the start of the IMP infusion and up to 72 hours after the end of IMP infusion)
  - Related TEAEs or temporally associated TEAEs to IMP
  - TEAEs leading to permanent discontinuation of IMP
  - TEAEs leading to withdrawal from study
  - TEAEs leading to IMP dose interruptions
  - AESIs
  - AESIs related to IMP
  - Temporally associated AESIs (defined as an AESI with an onset between the start of the IMP infusion and up to 72 hours after the end of IMP infusion)
  - Serious TEAEs
  - Serious TEAEs related to the IMP
  - Serious TEAEs related to corticosteroid treatment
  - Temporally associated serious TEAEs
  - Fatal serious TEAEs
- 
- The following descriptive tables will be generated for TEAEs, including number of subjects, percentages of subjects, the number of events, and TEAE rate per time at risk. Analyses marked with \* will also be provided for the subgroup of Japanese subjects:
    - TEAEs by System Organ Class (SOC) and Preferred Term (PT)  
Note: This table will also be provided by age group (<65 year,  $\geq$ 65 years)
    - TEAEs by SOC, PT, and maximum severity\*
    - Causally related TEAEs by SOC and PT\*
    - Temporally associated TEAEs by SOC and PT\*
    - Causally related TEAEs or temporally associated TEAEs by SOC and PT
  

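### Serious worsening of dermatomyositis is kept out of the adverse event data, and no by-arm count of it, or of all-cause deaths, is planned in its place

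*Protocol*

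**What the plan says.** **Adverse event definition.** Protocol Section 9.1.1 makes the exclusion twice. Its list of what may be an adverse event includes "Exacerbation (ie, an increase in the frequency or severity) of a pre-existing condition, with the exception of DM". Its list of what is not one includes "Any worsening of DM including worsening of DM that meets serious criteria (eg, hospitalization"). Hospitalization is the only example given. Death and life-threatening events are also seriousness criteria in Section 9.1.2, where the rule for death is "The event must be the cause of death for the SAE to meet this serious criterion".

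**Safety tables.** SAP Section 11.2 says "TEAEs are defined as AEs started after the start of the first infusion of IMP". The overview rows for serious, fatal and discontinuation events are built on that definition. The percentage of subjects with serious TEAEs and the serious TEAE rate per time at risk are named secondary endpoints for objectives 2, 3 and 4 (Protocol Section 2.2.4, SAP Table 1). The only row for deaths is "Fatal serious TEAEs".

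**Monitoring committee.** Protocol Section 3.8.2: "The IDMC will receive notification of all serious adverse events (SAEs), AESIs, and deaths reported throughout the study". The committee also reviews compiled efficacy and safety data for Study Periods 1 and 2. SAP Section 4.6.3 says it does not review Study Period 3 data.

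**DOW.** SAP Section 8.2.17 begins "A subject who meets at least 1 of the following 3 criteria on 2 consecutive study visits at least 2 weeks apart". All three criteria are thresholds on core set measures; hospitalization and death are not among them.

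**Passages without the exclusion.** The disposition part of SAP Section 7.4 says that "When either treatment or the study is discontinued due to an AE or death", the corresponding adverse event is collected. SAP Section 11.6.3 sends clinically significant deteriorations on physical examination to the adverse event form. Neither makes an exception for DM.

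**The concern.** Keeping routine flares out of the adverse event data is an ordinary choice in a trial where the disease is the efficacy outcome. The difficulty is with the serious ones. Protocol Section 1.4 names disease flare as a potential risk both of placebo and of failure of IgPro20. The MDAAT counts myocarditis, arrhythmia and active interstitial lung disease as DM activity, and its examples of maximal activity involve ventilatory support and intensive care (SAP Figure 9). Such an event is an SAE if the site attributes it to something else, and no adverse event at all if the site attributes it to DM. Neither document describes adjudication of that judgement.

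What is at stake is the completeness of the safety comparison in Study Period 1 and of the description afterwards. If serious worsening is commoner on placebo, leaving it out hides a benefit of IgPro20. If it is commoner on IgPro20, leaving it out hides a harm. A reader of the planned tables could not tell which.

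**Working it through.** The point rests on definitions, so the check is to trace one event through the plan. Take a subject admitted to hospital for a DM flare.

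1. **Adverse event?** No (Protocol 9.1.1). It is therefore not an SAE and not a TEAE (SAP 11.2), and it does not enter the serious-event percentage or rate.
2. **Another safety table?** SAP Section 11 covers exposure, adverse events, events of special interest, laboratory values, vital signs, ECG, physical examination, hemolysis and Wells' scores. The laboratory tables include muscle enzymes, which may move with a flare but do not show an admission. No table counts DM hospitalizations or all-cause deaths.
3. **DOW?** Not necessarily. Scheduled core set visits run at Weeks 5, 9, 13, 17, 21 and 25, so consecutive visits are (9 − 5) × 7 = 28 days apart (nominal). Confirmation takes about 4 weeks on scheduled visits, or at least 2 weeks with an unscheduled one. An acute admission that resolves, or a subject who leaves, need not meet it.
4. **Primary endpoint?** If the subject is rescued or withdraws before Week 25 for a reason unrelated to the Ukraine war, the result is non-response (SAP 10.2). That is the same code as a stable subject whose TIS stayed below 20. Protocol 3.3.1 itself notes that TIS cannot separate no change from worsening.
5. **Disposition?** Withdrawals are tabulated by primary reason (SAP 9.1). The eCRF list of reasons is not in the documents, and a subject who is admitted but stays in the study does not appear there.
6. **Monitoring committee?** A non-fatal DM admission is not an SAE, need not be an event of special interest and is not a death, so it triggers no notification. A death does.
7. **Study Period 3?** DOW is not scheduled. Four of the six core set measures are collected every 24 weeks, and also at end-of-year, unscheduled and end-of-period visits. The committee does not review the data.

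Now let the event be fatal. Section 9.1.1 read with 9.1.2 implies no adverse event. SAP 7.4 implies one is collected, and SAP 11.6.3 could also produce one. The documents do not say which governs, so entry in the fatal row may depend on the site.

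**Size.** The plan states no rate, so there is no figure to reproduce. With 63 subjects per arm, one omitted subject with no other serious TEAE is 1/63 = 1.6 percentage points. If a such subjects are omitted on IgPro20 and b on placebo, the difference between arms shifts by (a − b)/63. As an assumption only, for a − b from 1 to 5 the shift is 1/63 = 1.6 to 5/63 = 7.9 points. If a = b, both percentages are too low but the difference is unchanged.

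**The case against.** The best defence is that these subjects do not vanish. Withdrawal or rescue before Week 25 counts as treatment failure, apart from war-related withdrawal. Stopping IMP in Study Periods 1 or 2 triggers the full Week 53 assessments. Unscheduled visits can collect core set measures. One sensitivity analysis sets subjects who die in Study Period 1 to non-responder, so deaths must be identifiable. The committee sees efficacy data for Study Periods 1 and 2. In Study Period 3, a subject showing clinical deterioration leaves the study with a recorded reason and a closing assessment, and corticosteroid use is analyzed.

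All of that stands, and it rules out two stronger readings that a reader might infer:

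- **That DM deaths appear in no safety table.** Section 9.1.1 gives only hospitalization as its example, and SAP 7.4 points the other way for deaths. Deaths are notified to the committee as a separate item with no DM exception, and may show in disposition.
- **That the efficacy analysis misses these subjects.** Most who withdraw or are rescued before Week 25 are counted as failures.

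What the defence does not supply is a count. None of these routes separates a serious DM worsening from ordinary non-response, a milder flare or an unspecific withdrawal, and none gives the number by arm. The protocol's expectation of few flares meeting DOW (Section 3.3.1) suggests the number may be small, but it concerns DOW rather than admissions or deaths.

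**Conclusion.** The point holds as a cheap improvement. By the current text, DM worsening that meets a seriousness criterion is outside the SAE and serious-TEAE results, and no by-arm table of it or of all-cause deaths replaces them. Nothing here affects the primary test, its power or its error rate. The handling of a fatal DM worsening is an unresolved conflict between Protocol 9.1.1 and SAP 7.4 and 11.6.3, not a proven omission.

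The size is unknown. The figure of 1.6 percentage points per subject assumes 63 treated subjects per arm and no other serious TEAE in that subject. How many such subjects there will be, and whether the arms differ, cannot be judged from the documents. The gap is widest in Study Period 3, although there it affects description rather than a comparison.

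**What to change.** - **Protocol 9.1.1:** keep non-serious DM worsening out of adverse events. Require DM worsening that meets a seriousness criterion to be recorded on the eCRF, exempt from expedited reporting if the sponsor wishes and the applicable rules allow.
- **SAP 11.2:** add two rows by treatment and period, each with a listing: serious DM worsening (including fatal), and all-cause deaths. Keep them apart from the planned serious-TEAE rows so that those rates are unchanged. Comparing the all-cause row with the fatal serious TEAE row shows how many deaths carry no adverse event.
- **Monitoring committee:** supply both for Study Periods 1 and 2.
- **Reconcile** Protocol 9.1.1 with SAP 7.4 and 11.6.3, stating whether a fatal DM worsening, or a clinically significant deterioration due to DM, generates an adverse event record.

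The cost is a protocol wording change, a few extra forms, two table rows with listings, and some disease-related events in the safety database. If adopted mid-study, ascertainment would differ before and after the change unless earlier events are collected retrospectively from withdrawal and source records; the report should say which was done.
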